The research will add to existing research by identifying and measuring potential mechanisms of change for negative symptoms (i.e., defeatist attitudes, reflective functioning, stigma and depression). It will also add to the existing evidence base by measuring whether the cognitive biases addressed in MCT lead to changes in the wider conceptualisation of metacognition used elsewhere and whether the promising results seen in the feasibility study of MCT Minus (Swanson et al., 2021) can be replicated in a randomised controlled trial (RCT) with a control group and a blinded assessor. We also hope to replicate the findings of a previous study by Shan et al. 2020, where MCT was found to be related to the modulation of default-mode network (DMN) homogeneity in schizophrenia, an area thought to be involved in self- and other-reflectivity.

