#### **5. Project description**

##### **5.1. Participants, sample size, settings and ethics**

Eligible participants will be over the age of 18 with a diagnosis of schizophrenia, delusional disorder or non-affective psychosis in Region Sörmland, Region Västmanland and Region Uppland. Exclusion criteria will be evidence of severe organic brain dysfunction or a learning disability, difficulty with the Swedish language, visual and/or hearing impairment, or being unable or unwilling to provide written informed consent. Clinical teams will be approached by [name] or a research assistant and asked to inform suitable patients about the study. The research assistant will then meet the subjects and inform them (both orally and written) prior to gaining written consent. Subjects who have been allocated to the control group (i.e. supportive counselling) will be offered metacognitive training after the trial has finished if they request this. We have used t/z-test, with a power of 0,85, and a significance level of 0,05, to calculate sample size. In order to find a difference of 4 units on CAINS (as a change in total score of 4 points has been found to show a true change at a 95% confidence level in previous research (Laraki et al., 2022)), 41 participants in each arm will be needed. We will aim to recruit 45 in each arm to allow for drop-out, group heterogeneity and to make future analysis (e.g. on the effect of medication) possible. Ethical approval will be applied for at the Etikprövningsmyndigheten.

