##### **5.3. Outcome measures**

This study will use a combination of interviews and self-rated questionnaires to assess negative symptoms. The primary outcome measures will be the Clinical Assessment Interview for Negative Symptoms (CAINS) (Forbes et al., 2011), the Motivation and Pleasure Scale—Self-Report (MAP-SR) (Llerena et al., 2013), and the Positive and Negative Syndrome Scale (PANSS) (Kay et al., 1987) (with the PANSS negative factor proposed by Wallwork et al. (2012)). The CAINS was chosen as it has been developed to measure negative symptoms as defined by the NIMH consensus development conference (i.e., blunted affect, alogia, anhedonia, asociality and avolition) (Kumari et al., 2017). (We replaced the Brief

Negative Symptom Scale (BNSS) (Kirkpatrick et al., 2010) with CAINS as the BNSS has not been validated or translated into Swedish).

To identify and measure mechanisms of change, four measures will be used: the Dysfunctional Attitudes Scale (DAS) (Weissman & Beck, 1978) to measure the severity of defeatist attitudes; the Reflective Functioning Questionnaire (RFQ-8) (Fonagy et al., 2016) to assess metacognitive capacity; the Calgary Depression Scale for Schizophrenia (CDSS) (Addington et al., 1990) to measure depression; and the Internalized Stigma of Mental Illness Scale-9 (ISMI-9) (Hammer & Toland, 2017) to measure stigma. Finally, the World Health Organization (WHO) Disability Assessment Schedule (WHODAS) 2.0 (WHO, 2010) will be used as this has been suggested to be a more reliable measure than the Global Assessment of Functioning (GAF) (American Psychiatric Association (APA), 1987) for assessing a person's overall functioning (Gspandl et al., 2018).

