#### **5.4. Procedure**

Written informed consent, relevant demographic information and baseline measures will be completed before beginning the intervention. The Motivation and Pleasure Scale—Self-Report (MAP-SR) (Llerena et al., 2013) will be used to certify that some level of negative symptoms exist prior to the intervention. The patients will be randomised to either MCT Minus and treatment as usual or supportive counselling combined with treatment as usual using an online calculator. Pre-, post-, and follow-up assessments will be conducted by a research assistant who is blind to group allocation. Exit interviews will be held after completing the intervention where a standardized interview schedule (with open-ended questions) will be applied to minimize variations in questions asked while retaining enough flexibility to assess individual experiences (Patton, 1987). The head of the division psychiatry in the regional health board (Region Sörmland) has approved the study and there are structures (e.g. funding, research time, support from clinicians and managers) that would facilitate recruitment and feasibility.

During the pre and post assessment visits, the patients will also undergo a magnetic resonance imaging (MRI) investigation, including anatomical (T1-weighted) imaging, resting-state functional MRI to assess changes in default mode network connectivity after the active compared to control intervention, and additionally diffusion weighted imaging (DWI) and MR spectroscopy (MRS) to relate the functional connectivity findings to structural connectivity and prefrontal glutamate levels.

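### MAP-SR is a self-rated primary outcome that the assessor blinding does not protect, and the protocol does not rule out an efficacy claim resting on it alone

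*Protocol*

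**What the plan says.** Protocol section 5.3 announces mixed modes of measurement: "This study will use a combination of interviews and self-rated questionnaires to assess negative symptoms". It then opens the list of primary outcomes with "The primary outcome measures will be the Clinical Assessment Interview for Negative Symptoms (CAINS", continues with "the Motivation and Pleasure Scale—Self-Report (MAP-SR" and ends with PANSS, scored by its negative factor. The three are not ranked, and no rule says whether one, some or all of them must be positive.

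On blinding, section 5.4 says: "Pre-, post-, and follow-up assessments will be conducted by a research assistant who is blind to group allocation". Section 1 presents the same feature as an advance on the feasibility study, whose results it hopes "can be replicated in a randomised controlled trial (RCT) with a control group and a blinded assessor". Neither section says that patients are blind. The last paragraph of section 2.2 mentions blinding without saying who is blind.

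On the arms, section 5.4 has patients "randomised to either MCT Minus and treatment as usual or supportive counselling combined with treatment as usual". Section 5.1 adds that controls "will be offered metacognitive training after the trial has finished if they request this". The sample size in section 5.1 is calculated for a CAINS difference only.

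**The concern.** For an interview scale, a rater who does not know the arm is a real safeguard. For MAP-SR the rater is the patient, so a blind research assistant who administers the form leaves the source of the rating unmasked. One of the three primary outcomes is therefore outside the protection that the protocol offers as its gain in rigour.

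Patients will probably know which treatment they are in. MCT Minus is eight individual sessions with psychoeducation and strategies aimed at particular cognitions (section 5.2); the comparator is supportive counselling. If patients in one arm expect more from their treatment, their self-ratings can differ without any difference in symptoms. A MAP-SR difference with nothing on CAINS or PANSS could then be reported as a primary result of a trial described as blinded.

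The problem is bias, so dividing the significance level among the three outcomes lowers the error rate but does not remove the cause.

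**Working it through.** **The plan's own figure.** Section 5.1 gives 41 per arm for a 4-point CAINS difference, power 0.85, significance level 0.05. It states no SD and no sidedness. With the two-sided normal formula n = 2 × (1.960 + 1.036)² × SD² / 4², an SD of 6 gives 2 × 8.98 × 36 / 16 = 40.4, so 41. The figure thus fits an unstated SD of about 6, and MAP-SR plays no part in it.

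**Chance of a false MAP-SR result.** Inputs: 41 per arm needed and 45 to be recruited, level 0.05 (section 5.1), taken as two-sided. Assumptions: no true effect, and a between-arm reporting shift of b SD on MAP-SR. The documents give no value for b, so a range is shown. The test is a two-sample t-test, the family used in section 5.1, with noncentrality b × √(n/2) and 2n − 2 degrees of freedom. √(41/2) = 4.528 and √(45/2) = 4.743. The chances below are for a significant result favouring MCT Minus.

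| b (SD) | Noncentrality, n = 41 | Chance, n = 41 | Noncentrality, n = 45 | Chance, n = 45 |
|---|---|---|---|---|
| 0 | 0 | 2.5% | 0 | 2.5% |
| 0.1 | 0.453 | 6.5% | 0.474 | 6.8% |
| 0.2 | 0.906 | 14% | 0.949 | 15% |
| 0.3 | 1.358 | 27% | 1.423 | 29% |
| 0.4 | 1.811 | 43% | 1.897 | 47% |

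The planned analysis is a repeated measures ANCOVA (section 6.1), so b should be read in units of the SD of the outcome as analysed.

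**What this means for the trial as a whole.** The answer depends on the success rule. Three normal test statistics were simulated (1,000,000 draws, 41 per arm, assumed pairwise correlation 0.5, shift on MAP-SR only).

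| Rule | b = 0 | b = 0.2 | b = 0.3 | b = 0.4 |
|---|---|---|---|---|
| Any of three significant, each at two-sided 0.05 | 12.5% | 21% | 33% | 49% |
| Any of three significant, Bonferroni | 4.5% | 9% | 17% | 30% |
| All three significant, favouring MCT Minus | 0.15% | 0.34% | 0.40% | 0.44% |
| CAINS alone, two-sided 0.05 | 5% | 5% | 5% | 5% |

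Under the all-three rule the chance stays below 1% at every correlation tried, from 0 to 0.7. Under the any-of-three rule it grows with b, and Bonferroni reduces it without restoring the nominal level. With CAINS as sole primary, a shift confined to MAP-SR has no effect on the primary error.

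**The case against.** The strongest reply is that nothing in the protocol is misstated. It never claims that patients are blind: section 1 and section 5.4 both confine blinding to the assessor, and section 5.3 says openly that self-rated questionnaires are used. That stands. Those two sections need no correction; only the mention of blinding in section 2.2 is loose.

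Second, the comparator is active. Both arms receive a psychological treatment on top of usual care, which is a standard way to narrow expectancy differences. This also stands as mitigation, and it makes the lower values of b more plausible. It does not show that b is zero.

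Third, a reader might infer that expectancy alone could make the trial a success. The documents do not support that. They state no success rule, the trial is sized on CAINS, a decision rule may sit in a statistical analysis plan that is not shown, and if all three outcomes had to be positive the risk would be below 1%. What remains is that the protocol, which fixes the primary outcomes, does not exclude a claim on MAP-SR alone.

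Fourth, two further arguments should carry little weight. The offer of metacognitive training to controls applies after the trial and on request, and nothing says that it affects answers. A change in self-report following psychoeducation may be response shift, but section 5.2 describes the cognitions as deliberate targets, so it may equally be the intended effect.

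Fifth, CAINS and PANSS ratings also draw on what the same patients say at interview. Blinding the assessor therefore gives those scales partial protection, while it gives MAP-SR none. The contrast is one of degree.

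**Conclusion.** The point holds in limited form. An unranked primary outcome is rated by patients who will probably know their treatment, and the only blinding described does not reach it. Under an assumed shift of 0.1 to 0.4 SD with no true effect, the chance that MAP-SR significantly favours MCT Minus rises from 2.5% to about 7% to 47% (41 to 45 per arm, two-sided 0.05). The size of the shift is an assumption without a source in the documents, and patients' awareness of their arm is an inference.

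The trial-level consequence is conditional: it arises only if MAP-SR alone can carry the efficacy claim. The finding is not that the protocol presents patients as blind or that expectancy by itself makes the trial positive. The use of MAP-SR at entry to confirm negative symptoms applies to both arms before treatment and adds no between-arm bias in itself.

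**What to change.** In section 5.3, name assessor-rated CAINS as the primary outcome and list MAP-SR as a secondary, unmasked self-report outcome. If the sponsor prefers to keep MAP-SR among the primaries, the minimum is a sentence saying that a MAP-SR difference without support from an assessor-rated scale does not establish efficacy and will be reported as self-report only.

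In section 2.2, say that the assessor is blind, in line with section 1. Sections 1 and 5.4 can stay as they are.

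The cost is protocol wording. MAP-SR is still collected and reported, and the 41 per arm does not change because it was calculated on CAINS alone. The downside is that the patient-reported result can no longer carry the primary claim by itself. The change also reduces the exposure to bias without removing it, since interview ratings depend in part on what patients report.

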#### **5.4. Procedure**

Written informed consent, relevant demographic information and baseline measures will be completed before beginning the intervention. The Motivation and Pleasure Scale—Self-Report (MAP-SR) (Llerena et al., 2013) will be used to certify that some level of negative symptoms exist prior to the intervention. The patients will be randomised to either MCT Minus and treatment as usual or supportive counselling combined with treatment as usual using an online calculator. Pre-, post-, and follow-up assessments will be conducted by a research assistant who is blind to group allocation. Exit interviews will be held after completing the intervention where a standardized interview schedule (with open-ended questions) will be applied to minimize variations in questions asked while retaining enough flexibility to assess individual experiences (Patton, 1987). The head of the division psychiatry in the regional health board (Region Sörmland) has approved the study and there are structures (e.g. funding, research time, support from clinicians and managers) that would facilitate recruitment and feasibility.

During the pre and post assessment visits, the patients will also undergo a magnetic resonance imaging (MRI) investigation, including anatomical (T1-weighted) imaging, resting-state functional MRI to assess changes in default mode network connectivity after the active compared to control intervention, and additionally diffusion weighted imaging (DWI) and MR spectroscopy (MRS) to relate the functional connectivity findings to structural connectivity and prefrontal glutamate levels.

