## 1. Purpose and aims

There is a clear rationale for developing interventions targeting negative symptoms of schizophrenia as negative symptoms are a stronger indicator of current and future functioning than positive symptoms (Velligan et al., 2015) and because they respond poorly to medication (Veerman et al., 2017) and existing psychological interventions (Fusar-Poli et al., 2015). This is reflected in the National Institute of Mental Health (NIMH)- Measurement and Treatment Research to Improve Cognition in Schizophrenia (MATRICS) consensus statement (Kirkpatrick, Fenton, Carpenter, & Marder, 2006) that emphasised that persistent negative symptoms represent an unmet therapeutic need for patients suffering from schizophrenia.

The purpose of this study is to evaluate, in a scientific manner, the intervention developed by Swanson et al. 2021: Metacognitive Training (MCT) Minus. This intervention adapted MCT to target negative symptoms in psychotic disorders (e.g. schizophrenia, schizoaffective or non-affective functional psychosis) as the original version of MCT (Moritz & Woodward, 2007) focused exclusively on positive symptoms. The specific aim is to study whether MCT Minus is a promising treatment for the intended population in terms of:

- Reductions in negative symptoms as measured by the Clinical Assessment Interview for Negative Symptoms (CAINS) (Forbes et al., 2011), the Motivation and Pleasure Scale- Self-Report (MAP-SR) (Llerena et al., 2013) and the Positive and Negative Syndrome Scale (PANSS) (Kay et al., 1987)
- Reductions in severity of defeatist attitudes as measured by the Dysfunctional Attitudes Scale (DAS) (Weissman & Beck, 1978)
- Improvements in reflective ability as measured by the Reflective Functioning Questionnaire (RFQ-8) (Fonagy et al., 2016)
- Reduction in internalised stigma as measured by the Internalized Stigma of Mental Illness Scale-9 (ISMI-9) (Hammer & Toland, 2017)
- Reductions in depression as measured by the Calgary Depression Scale for Schizophrenia (CDSS) (Addington, Addington, & Schissel, 1990)
- Improved functioning as measured by the World Health Organization (WHO) Disability Assessment Schedule (WHODAS) 2.0 (WHO, 2010)

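### Do sections 5.1 and 5.4 of the protocol disagree on who may be randomised?

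*Protocol*

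**What the plan says.** All references are to the protocol.

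- **Section 5.1, inclusion:** "Eligible participants will be over the age of 18 with a diagnosis of schizophrenia, delusional disorder or non-affective psychosis".
- **Section 5.1, exclusion:** the list begins "Exclusion criteria will be evidence of severe organic brain dysfunction or a learning disability, difficulty with the Swedish language" and goes on to sensory impairment and consent. Absence of negative symptoms is not on it.
- **Section 5.4, check:** the MAP-SR "will be used to certify that some level of negative symptoms exist prior to the intervention". No score is given for what counts, and nothing is said about a patient who does not reach it.
- **Section 5.4, timing:** "baseline measures will be completed before beginning the intervention". The sentence after the MAP-SR check describes randomisation, and the one after that reads "Pre-, post-, and follow-up assessments will be conducted by a research assistant who is blind to group allocation".
- **Section 1, target:** "This intervention adapted MCT to target negative symptoms in psychotic disorders", followed in brackets by "e.g. schizophrenia, schizoaffective or non-affective functional psychosis".
- **Section 5.1, size:** "41 participants in each arm will be needed", with a recruitment aim of 45 per arm.

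**The concern.** Negative symptoms are the treatment target, and all three primary outcome measures assess them. Yet the section that sets out eligibility does not require them. Under section 5.1 alone, a patient with schizophrenia and no negative symptoms may enter. Under section 5.4 the same patient should not proceed. Staff who worked from one section only could admit different patients.

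Timing adds to the worry. Both the check and the baseline measures are tied to the start of the intervention, not to randomisation. The pre-assessment is also covered by the statement that the assessor is blind to allocation, which could suggest that allocation already exists by then. If the check fell after allocation, a patient who failed would either be removed, so that the groups compared are no longer those randomised, or be kept, so that the check does nothing.

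Finally, section 1 names schizoaffective psychosis separately from non-affective psychosis, while section 5.1 does not name it. It could seem to be part of the target but barred from entry.

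**Working it through.** **Step 1. Sections 5.1 and 5.4 side by side.** Section 5.1 gives necessary conditions (age, diagnosis, no exclusion). Section 5.4 adds one more (some negative symptoms on the MAP-SR). Nothing in section 5.1 says that a patient who meets its list must be randomised whatever the check shows, and it asks clinical teams to inform only suitable patients. The two statements can both hold: the patients who enter are those who satisfy both. What is absent is the cross-reference, the score and the consequence of failing.

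**Step 2. Order of events in section 5.4.** The paragraph runs as follows:

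1. consent, demographic information and baseline measures;
2. the MAP-SR check;
3. randomisation to the two arms;
4. blinded pre-, post- and follow-up assessments;
5. exit interviews.

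The check is placed before randomisation. The blinding sentence covers all three assessments in one phrase and says who carries them out. It does not say that allocation has happened by the first of them. An assessor at a visit before randomisation is blind in any case.

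**Step 3. Consequence of that order.** A patient who fails is not randomised. The two arms are random halves of those who passed, so the between-arm difference is unbiased. The MAP-SR is both the entry check and a primary outcome, so a threshold would bring regression to the mean into the change within each arm. It would do so in both arms alike and would not affect their difference.

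**Step 4. Diagnosis lists.** Section 1 opens its list as examples and describes what the adapted intervention is aimed at. It also leaves out delusional disorder, which section 5.1 admits. It is therefore not exhaustive and is not an entry list; section 5.1 is.

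**Step 5. What the less natural reading would cost.** Inputs from section 5.1: difference δ = 4, α = 0.05, power 0.85, n = 41 per arm, aim 45 per arm. No SD and no sidedness are stated, so 41 cannot be reproduced forwards. The SD is solved backwards from it.

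- Margin: 45 − 41 = 4 per arm; 4/45 = 8.9%; 8 in total.
- SD for a two-sided z-test: δ√(n/2)/(z₀.₉₇₅ + z₀.₈₅) = 4 × √20.5/(1.960 + 1.036) = 18.11/2.996 = 6.04.
- SD for a one-sided z-test: 18.11/(1.645 + 1.036) = 6.75.
- SD for t-tests, solved numerically: 5.97 two-sided, 6.70 one-sided.
- Power at n per arm (two-sided z): Φ(δ/(SD√(2/n)) − 1.960). At n = 37: 4/(6.04 × 0.2325) = 2.85, and Φ(2.85 − 1.96) = 0.81.

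| Test | n = 45 | n = 41 | n = 37 | n = 35 |
|---|---|---|---|---|
| t, two-sided | 0.882 | 0.850 | 0.811 | 0.789 |
| z, two-sided | 0.881 | 0.850 | 0.812 | 0.791 |
| t, one-sided | 0.878 | 0.850 | 0.816 | 0.796 |
| z, one-sided | 0.878 | 0.850 | 0.817 | 0.797 |

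The columns for 37 and 35 are assumed losses of 8 and 10 per arm from any cause. The protocol gives no failure rate for the check. These losses arise only if failures are removed after randomisation; if the check comes first, none of them does.

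**The case for a change.** The strongest case for a change is that eligibility belongs in the protocol rather than in an analysis plan, and that the criterion missing from section 5.1 is the one that defines this trial's population. Patients without negative symptoms have little room to improve on the primary outcomes. If the check were ignored, the effect would be diluted. As an illustration (two-sided z, SD 6.04, no effect in such patients), a share of 10% would turn a difference of 4 into 4 × 0.9 = 3.6 and cut power at 45 per arm from 88% to 81%; a share of 20% would cut it to 71%. Adding the criterion to section 5.1 and the words before randomisation to section 5.4 would cost little.

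Part of this stands. The cut-off and the consequence of failing are unwritten, the timing is loosely worded, and section 5.1 does not say expressly whether schizoaffective disorder is in or out. But the dilution figures describe a trial in which section 5.4 is disregarded, and the documents give no share of such patients.

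The proposed wording also gains little. It has to leave the threshold blank for the sponsor, or fall back on any score short of the symptom-free end of the MAP-SR. That fallback is already the literal sense of section 5.4 and would turn away few patients. Nor would the trial report be unable to describe its population: CAINS, MAP-SR and PANSS are primary outcome measures, so their baseline values can show how severe negative symptoms were at entry.

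**Conclusion.** The concern does not call for a change. Sections 5.1 and 5.4 are incomplete when read apart, but they are compatible when read together. The order of section 5.4 puts the MAP-SR check before randomisation, and on that reading there is no bias between the arms and no loss of power. Section 1 gives examples of what the intervention targets and does not compete with the entry list in section 5.1.

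What remains is an unstated score, consequence and cross-reference, which trial staff can settle without altering the design. This rests on two assumptions: that staff apply both sections, and that they follow the order in which section 5.4 is written. If failures were instead removed after allocation, 4 per arm would exhaust the recruitment margin. That is the less likely reading, and it should not decide the matter.

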##### **5.2. Intervention**

The original MCT intervention was adapted to negative symptoms by incorporating psychoeducation and strategies to target the cognitions suggested by the cognitive model (Beck et al., 2009) to be implicated in the development and/or maintenance of negative symptoms (see Table 1). Although some of the strategies have traditionally been used to target positive symptoms, it is assumed that the same reasoning styles lead to negative symptoms through the dysfunctional cognitions discussed previously (e.g., jumping to conclusions in regard to social rejection and a dysfunctional attribution style reinforcing social withdrawal). Metacognitive training for negative symptoms consists of eight sessions, delivered individually as there is evidence indicating that this approach may lead to stronger effect sizes than delivery in a group format (Liu et al., 2018). The developer of MCT ([name]) approved the modification.

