## **6.2. Qualitative data**

Thematic analysis (Braun & Clarke, 2006) will be used to analyse the qualitative data. The interviews will be transcribed and transcripts will be read multiple times for familiarity with the material and to generate an overview of the responses (Mairs et al., 2011). The recordings will then be analysed with thematic analysis conducted according to a standard format (i.e., exploring the feasibility of the intervention and potential mechanisms of change). Themes will be developed, labelled and reviewed to assure that they are representative of the data set. This analysis will be undertaken by the primary researcher and discussed with other research collaborators.

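### Exit interviews are tied to completing the intervention, with no interview stated for patients who stop early, although they are to inform feasibility

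*Protocol*

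**What the plan says.** Section 5.4 of the protocol fixes the timing of the qualitative interview: "Exit interviews will be held after completing the intervention where a standardized interview schedule (with open-ended questions) will be applied". The schedule is meant "to minimize variations in questions asked while retaining enough flexibility to assess individual experiences".

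Section 5.2 sets the length of what has to be completed: "Metacognitive training for negative symptoms consists of eight sessions, delivered individually". It does not say how many sessions count as completion.

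Section 6.2 gives the transcripts two uses under the thematic analysis: "exploring the feasibility of the intervention and potential mechanisms of change".

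Section 5.1 anticipates losses: "We will aim to recruit 45 in each arm to allow for drop-out, group heterogeneity", and it names later analyses as a further reason for the margin.

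No section available for review offers an exit interview to a patient who stops before the end of the sessions, or asks for the reason for stopping.

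**The concern.** Whether patients can and will get through the sessions is a central part of feasibility. Those who stopped are the best informants on that question. If the interview is reached only by finishing, their accounts never enter the transcripts, and themes on feasibility and on mechanisms of change are built from those who stayed. That selection leans towards a favourable picture whenever the experience of stoppers differs for the worse.

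The analysis cannot repair this. Section 6.2 has the themes checked against the transcripts, and such a check cannot reveal a group that supplied no transcripts. Who is interviewed and when is a study procedure, fixed in section 5.4. It is not a detail that would normally be left to a statistical analysis plan.

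**Working it through.** The point rests mainly on reading sections against each other.

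1. **Trigger.** Section 5.4 places the interview after completion of the intervention. For the experimental arm, section 5.2 makes that eight sessions. A patient who leaves after, say, the third session has not met the condition as written.
2. **Contrast within section 5.4.** The blinded quantitative assessments at baseline, end of treatment and follow-up carry no condition of completion. The exit interview is the one element worded by reference to completing.
3. **Use.** Section 6.2 assigns the interviews to feasibility and mechanisms. Feasibility is the use most exposed to completer selection.
4. **Expectation of losses.** Section 5.1 allows for drop-out, so the protocol itself does not expect everyone to finish.
5. **Alternative route.** No section available for review gives a separate interview, or a record of reasons, for early stoppers. Section 7 was not in the copy reviewed and could bear on this.

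**What the figures can and cannot tell us.** The only relevant figures are 41 required and 45 recruited per arm.

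- Margin per arm: 45 − 41 = 4, and 4/45 = 8.9%. Over both arms this is 8 of 90.
- This is the whole margin, shared between drop-out, heterogeneity and later analyses. It is not a drop-out rate. It also concerns patients lost to the outcome analysis, which is a different event from stopping sessions.
- The number of patients without an interview under the literal reading is 45 × r per arm, where r is the share who stop early. No r is given. Under assumed values, 5% gives 2.25, 10% gives 4.5, 20% gives 9 and 30% gives 13.5 per arm.

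These are counts of possible missing interviews, not a measure of bias.

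For completeness, the 41 per arm cannot be reproduced directly because no standard deviation is stated. With a 4-point difference, power 0.85 and a two-sided level of 0.05 (sidedness assumed), solving backwards gives SD = 4 × √(41/2) / (1.960 + 1.036) ≈ 6.04. Nothing in this point depends on that value.

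**The case against.** The strongest reply is that the sentence in section 5.4 is about timing. The same section places consent and baseline measures ahead of treatment, so the words on the exit interview may simply mean the end of treatment. This stands in part: the protocol never says that the interview is for completers only or that stoppers are excluded. A reader might infer both, but neither is stated. What remains is that the sentence can be followed in two ways, and the literal one yields no interview for early stoppers.

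Second, feasibility is not among the specific aims in section 1, and section 2.2 attributes the feasibility question to the previous study of this intervention. That is correct and limits the weight of the point. Section 6.2 still names feasibility as a purpose of the interviews.

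Third, patients who stop are not shown to be lost to all evidence. The quantitative assessments, including depression and functioning, are not conditional on completion. That stands too, although a scale score is not an account of why someone left.

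Three stronger readings are tempting and should be resisted:

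- **That evidence on unwanted effects is being lost.** The protocol gives the interviews no such role. Section 6.2 names feasibility and mechanisms only. The interview schedule is not shown, so it cannot be faulted for lacking a question on distress. That patients stop because the sessions were distressing or unhelpful is also not in the text.
- **That the bias can be quantified.** Any rate of complaint among completers or stoppers would have to be invented, and thematic analysis produces themes, not prevalence.
- **That section 6.2 contradicts itself by promising representative themes.** The promise concerns fit to the transcripts, not to all randomised patients.

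**Conclusion.** The point holds as a modest, specific improvement. As written, section 5.4 links the exit interview to completing the intervention and states no provision for early stoppers, while section 6.2 relies on those interviews for feasibility and section 5.1 expects losses. Following the text literally gives feasibility themes drawn from completers.

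The direction of any distortion depends on the assumption that stoppers would describe the intervention less favourably. That is plausible but not documented. Its size cannot be derived. The consequence is confined to the qualitative component, and the comparison on the negative-symptom scales is unaffected. The conclusion also assumes that nothing in the section not available for review covers these patients.

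**What to change.** In section 5.4, replace the completion trigger with wording that offers the exit interview when the intervention ends for that patient, whether completed or stopped early, and record the reason for stopping if the patient gives one.

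In section 6.2, state how many interviewees were completers and how many stopped early, and note any themes specific to the latter. This needs one line on what is counted as completing. A full separate thematic analysis of stoppers is not needed, as their number may be very small.

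The cost is a few sentences and a few more interviews by the same staff. Some early stoppers will decline, so the gap will be narrowed and not closed; reporting the two counts lets readers see how far. The change should be made before recruitment starts.
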